Prospective Randomized Control Trail Evaluating Single Shot Exparel versus Indwelling Interscalene Catheter for Total Shoulder Replacements- A Pilot Study

Introduction:

Shoulder surgery, especially shoulder replacement surgery, is well known to involve severe postoperative pain. Regional anesthesia is often the most effective and safe modality for pain control, decreasing opioid consumption and its associated side effects and allowing for earlier rehabilitation necessary for improving shoulder surgery outcomes. (1, 2) Better analgesia, therefore, can reduce hospital length of stay, decrease costs, and improve overall patient satisfaction. For major shoulder surgeries, the interscalene nerve block is a well-recognized and efficient procedure for controlling pain. Having a continuous infusion of local anesthetics through an indwelling interscalene catheter is the best technique for pain control after shoulder surgery. (1) Our standard of care for total shoulder replacement surgeries involves placement of an indwelling interscalene catheter that is attached to an On-Q pump, which infuses a low dose local anesthetic at a set rate continuously until the catheter is removed usually on a postoperative day 2. The continuous infusion of local anesthetic through an indwelling catheter allows for a more prolonged nerve block and analgesia as compared to a single shot interscalene nerve block, whose analgesic duration depends on the local anesthetic and any additives given at the time of the block.

While placing an indwelling nerve catheter can prolong pain control, it can also have drawbacks and complications. While major complications like pneumothorax and hemidiaphragmatic paresis from interscalene continuous peripheral nerve blocks (CPNB) are rare, minor adverse effects associated with CPNBs may be more common. They include infection and anatomical damage to blood vessels and nerves due to the indwelling catheter. (3) In addition, catheters take a significantly longer time to set up and place than single shot blocks, which is important as there is often a rush to block patients and trying to get them into the operating room on time. Furthermore, the needle used for catheter placement is larger than the single shot needles, which creates more discomfort to patients during the nerve block. The catheter itself is taped around the entire sides and back of the patient's neck, which is also uncomfortable for patients. Because of how shallow the interscalene block is, the catheter is often found to be dislodged from operating room positioning, patient transport or movement, which negates the placement of the catheter. An indwelling catheter must also be followed up by the acute pain service team until the catheter is removed.

Exparel, or liposomal bupivacaine, is formulated to release low dose bupivacaine over 96 hours, and was recently approved by the FDA in April 2018 to be used in interscalene blocks. The sustained release of local anesthetic could theoretically act similarly to the continuous infusion of local anesthetic through an indwelling interscalene catheter, and could thus avoid the need for placement of a catheter. Current existing data, although inconclusive, has in some studies shown an equal analgesic effect as catheters. (4) As per pharmacy, the cost of the On-Q pump and the

local anesthesia needed for the pump together cost \$390 for each indwelling catheter placed, not including the cost of anesthesia and pharmacy supplies and labor. The cost of each 20 mL vial of Exparel is less at \$285 and, for a single shot nerve block, would avoid the extra costs and time needed for a catheter placement.

We would like to perform a prospective randomized controlled pilot study to examine the efficacy of single shot interscalene blocks using Exparel versus the traditional interscalene catheter used at our institution. The purpose of the study we are proposing is to determine if single shot interscalene nerve blocks using Exparel can provide equivalent or better analgesia than indwelling interscalene catheter in patients who undergo total shoulder replacement surgery. If so, single shot interscalene nerve blocks with Exparel may serve as a quicker, easier, cheaper, safer, and more comfortable alternative to placing indwelling interscalene catheters.

Hypothesis:

Single shot interscalene nerve blocks using liposomal bupivacaine provides superior analgesia than indwelling interscalene catheters for total shoulder replacements.

Primary Objective:

Patient opioid requirements at 24 hours in morphine equivalents

Secondary Endpoints:

-Intra-operative opioid requirements (morphine equivalents)

- 48-hour opioid requirements (morphine equivalents)
- -Patient pain scores in the PACU

Tertiary Endpoint:

-Hospital length of stay

Design and Methods:

This is a randomized controlled study in patients undergoing total shoulder replacement surgery. At our institution, these patients typically receive an indwelling interscalene catheter and undergo general anesthesia for the surgery. For this study, patients will be randomized into two groups: group 1 will receive an indwelling interscalene catheter, while group 2 will receive a single shot interscalene nerve block with liposomal bupivacaine.

Group 1 will receive an indwelling interscalene catheter placed posterior to C5-C6 nerve roots, and given 15 mL of 0.5% ropivacaine plain for the block with no superficial cervical block. The

On-Q pump will be set at a rate of 4 mL/hr. A maximum sedation of 2mg of midazolam and 100mcg of fentanyl may be used for the block.

Group 2 will receive a single shot interscalene nerve block using 20 mL of a mixture of 10 mL of Exparel and ten mL of 0.5% bupivacaine. A maximum sedation of 2mg of midazolam and 100mcg of fentanyl may be used for the block.

All nerve blocks and catheter placements will be performed under ultrasound guidance with an in-plane technique using a stimiplex needle, without twitch monitor, by a trained expert in the regional anesthesiology division. The study medications will be drawn up by the regional anesthesiologist performing the block.

All patients will undergo general anesthesia and receive the same intraoperative and postoperative analgesic regimen. Intraoperatively, patients may receive 100mcg of fentanyl for induction, 0.35mg/kg of ketamine before incision, 1g of IV acetaminophen if no contraindication and maximum of 2mg of hydromorphone. Postoperatively, patients will receive a hydromorphone PCA set at 0.2mg with a lockout of 6 min and no basal dose. Patients will also be ordered for 650mg acetaminophen every 6 hrs standing if no contraindication. To clarify, the study procedure will be done in addition to standard of care.

The consents will be available and given to patients by IRB approved personnel when they come in for their pre-op evaluation visit. Key personnel will explain the study to patients then. If patients would like more time to decide, they make take the consent home with them and have until day of surgery to sign and agree.

Inclusion Criteria:

- ASA 1, 2, and 3
- Ages 40-74
- Patients scheduled for total shoulder replacement

Exclusion Criteria:

- ASA 4 and 5
- Pre-existing pain disorder
- Regular consumption of chronic pain medication
- pregnant women
- any medical condition such as a clotting disorder
- anatomic abnormality that precludes use of an indwelling scalene catheter
- BMI >40
- Patient refusal
- Pre-existing diabetic neuropathy or Hemoglobin A1c >9
- Failed block

Randomization:

Subjects will be randomized on the day of the procedure. A 1:1 random allocation sequence will be used to assign patients to one of the two groups. Pre-sealed randomization envelopes will be opened just before performing the block. A physician or nurse that is not part of data collection and not directly involved in the care of the patient will prepare the drug according to the randomization allocation. A faculty member not directly involved in the study or patient care will maintain the randomization codes.

In case of emergency, the principal investigator or his designee will be able to obtain the randomization key. The IRB and DSMB will be notified of the date, time and reason for obtaining randomization key will be recorded

Statistical Analysis:

In this hypothesis-generating pilot study, we are assuming a large effect size between the groups. In our clinical audit, the average amount of opioid used by these patients is 29 ± 12 mg. For the sample size calculation, we are expecting a 50% difference in opioid consumption between the two groups. Based on a two-sided alpha of 0.05 and Type II error of 20% to achieve a clinically significant 50 % difference a total of 24 subjects needed to be studied. In order to accommodate the missing cases, we are increasing the sample size to 14 patients per group.

The primary endpoint of the study, 24-hour opioid requirements is a continuous variable a nonparametric Wilcoxon rank sum test will be used for the analysis. For all the secondary outcomes continues variable, will be analyzed similarly as the primary endpoint and categorical variables will be analyzed using chi-square analysis or Fischer's exact test. All the outcomes will be reported with 95% confidence interval. For all analysis, a p-value of 0.05 is considered as statistically significant. There will be no interim analysis for this study. As this is a hypothesisgenerating study with small sample size, all the analysis will be reported as unadjusted.

Data Management:

All information and patient follow up will be entered into a computer database to be maintained by the principal investigator or their designee. Information in the database will be tracked by the specific randomization code assigned to each patient, which ultimately corresponds to a particular arm of the study.

Risks and Benefits:

Exparel is a sustained-release formulation of bupivacaine and thus has similar safety profile as other local anesthetics commonly used for peripheral nerve blockade. It has been used in other peripheral nerve blockade without any significant side effect experienced by patients. As with any nerve block, potential complications including bleeding, infection, nerve damage and

damage to surrounding structures, and seizures may occur. However, with the use of ultrasound guidance by experienced providers, the overall risk of the procedure and the proposed study remains very low. (5, 6) On the other side, the indwelling catheter also has risks such as infection and anatomical damage to blood vessels and nerves.

Data Safety Monitoring Board:

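### Does the 48-hour opioid endpoint need a stated clock start and a rule for patients discharged before 48 hours?

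*Combined protocol and SAP*

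**What the plan says.** The Primary Objective is opioid use at 24 hours. The Secondary Endpoints add intra-operative use, PACU pain scores and "48-hour opioid requirements (morphine equivalents". The Tertiary Endpoint is "Hospital length of stay". Neither opioid window has a stated start, and nothing says whether block-sedation or intra-operative opioid counts towards it.

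Design and Methods prescribes one analgesic regimen for everyone during and after surgery. The only postoperative opioid it names is a PCA: "Postoperatively, patients will receive a hydromorphone PCA set at 0.2mg with a lockout of 6 min and no basal dose". Data Management says "All information and patient follow up will be entered into a computer database", without distinguishing the arms and without giving content or timing.

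The only timing clues are in the Introduction and concern usual catheter care. The pump runs "until the catheter is removed usually on a postoperative day 2", and "An indwelling catheter must also be followed up by the acute pain service team until the catheter is removed". No discharge time or typical stay is given.

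Statistical Analysis applies the Wilcoxon rank sum test to continuous secondary outcomes, as for the primary. On losses it says only: "In order to accommodate the missing cases, we are increasing the sample size to 14 patients per group".

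**The concern.** Day 2 is what this endpoint adds to the primary. If some patients go home before 48 hours and their later use is not collected, part of day 2 is unseen, and two teams could compute different totals from the same patients.

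The documents also give some reason to think observation might differ by arm. Catheter patients are followed by the pain service until removal, and no counterpart is described for the single-shot arm. The Introduction says better analgesia can shorten stay, and length of stay is itself an outcome. If single-shot patients left sooner and their later use counted as zero, the error would favour the stated superiority hypothesis.

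**Working it through.** **1. The plan's own figure.** Statistical Analysis gives mean 29 mg, SD 12 mg, a 50% difference, two-sided alpha 0.05 and 80% power.
- Difference = 0.5 × 29 = 14.5 mg; d = 14.5/12 = 1.208.
- Normal approximation: n = 2 × (1.960 + 0.842)² / 1.208² ≈ 10.8, so 11 per arm, 22 in total.
- Two-sample t-test: 11.79, so 12 per arm, 24 in total. This matches "a total of 24 subjects needed to be studied".
- Wilcoxon allowance: 11.79/0.955 = 12.35, so 13 per arm, inside the planned 14.
- Allowance for missing cases: 28 − 24 = 4, or 2 per group.

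The sample size is not in question here. No figure is stated for the 48-hour endpoint.

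**2. What the timing clues show.** Take surgery as day 0 and count calendar days (assumption). Surgery ending at 10:00 puts day 2 at 38 to 62 hours; ending at 18:00 puts it at 30 to 54 hours. The 48-hour point lies inside both ranges, so catheter removal may fall on either side of it. Removal is not discharge in any case.

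**3. How much would be unseen.** If n of 14 in one arm leave at hour h, the unseen share of that arm's day-2 patient-hours is (n/14) × (48 − h)/24. With flat day-2 use equal to r times day-1 use, the arm mean falls by that share × r/(1 + r).
- n = 1, h = 36, r = 0.5: share 3.6%, mean falls 1.2%.
- n = 2, h = 28, r = 1: share 11.9%, mean falls 6.0%.
- n = 7, h = 28, r = 1: share 41.7%, mean falls 20.8%.

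**4. False-positive rate with no true difference.** Assumptions: day-1 use gamma with mean 29 and SD 12 mg (the audit figure taken as a 24-hour amount, since its window is not stated); r = 0.5 or 1; 14 per arm; two-sided Wilcoxon; leavers in one arm only; discharge at 28 or 36 hours; 6,000 runs (8,000 for exclusion). With no leavers the rate was 4.0%.

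| Leavers of 14 | In-hospital use only | Excluded: exactly the lowest users | Excluded: ranking noise SD 12 mg | Excluded: ranking noise SD 24 mg |
|---|---|---|---|---|
| 1 | 4.2% to 4.7% | 6.4% | 5.7% | 5.0% |
| 2 | 4.1% to 5.7% | 9.7% | 6.7% | 4.9% |
| 4 | 5.1% to 9.5% | 21.3% | 11.6% | 6.9% |
| 7 | 6.9% to 25.5% | 41.5% | 19.3% | 10.2% |

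If day-2 use tapers linearly to zero, in-hospital counting gives 4.4% to 5.4% for 1 or 2 leavers and 4.6% to 18.4% for 4 or 7. The two mishandlings err in opposite directions: truncation makes the arm with early leavers look better, while dropping its lowest users makes it look worse.

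**5. More extreme discharge patterns.** These used discharge at 24, 30 or 36 hours, later use set to zero and 4,000 runs. If a fraction f of the single-shot arm leaves at hour T and all catheter patients stay, the expected shortfall is f × (48 − T)/24 × r × 29 mg.
- f = 0.5: from 0.5 × 0.5 × 0.5 × 29 = 3.6 mg to 0.5 × 1 × 1 × 29 = 14.5 mg; simulated false-positive rate 7% to 38%.
- f = 1: from 7.25 to 29 mg; rate 17% to 97%.
- Half of each arm leaving: bias within 0.3 mg of zero; rate 4% to 5%.

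**6. Clock start.** No simulation is needed. Any one origin, with one rule on which opioids count, applied alike to both randomised arms gives a fair comparison. The choice alters what is being measured, not the validity of the test, unless it is made after seeing the results.

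**The case for a change.** The strongest case for acting is that absent discharge times make the size unknown, not small, and that opioid use at home cannot be recovered reliably once the moment has passed. Settling the matter in writing would cost two or three sentences and a brief contact with any early leaver among 28 patients. The clock start is also missing for the primary, so the gap is not confined to a lesser endpoint.

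Much of this stands. The size is unknown, and the primary does share the missing origin. What does not stand is the step from silence to bias. The plan nowhere tells staff to stop counting at discharge or to drop early leavers, and the endpoint's name says the opposite. The implied difference between arms leans on an Introduction remark about the drawbacks of catheters, which is not a data-collection procedure; the trial's own methods describe the same regimen for all patients and the recording of follow-up without regard to arm. Length of stay already requires discharge data, so early leavers will be visible by arm, with at most the hour missing. The alarming rates come from assumed patterns, such as a whole arm leaving early against none of the other, that no section supports.

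**Conclusion.** No change to the plan follows. This is missing operational detail that a competent team fills sensibly: one clock for both windows, one list of counted opioids, and use collected to 48 hours in both arms.

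The effect on the 48-hour comparison is nil if nobody leaves before 48 hours, and in-hospital-only counting causes no bias if early discharge is balanced. With 1 or 2 leavers in one arm and in-hospital use only, the false-positive rate stays at 4% to 6%. Losing two patients per group, the plan's own allowance, costs at most about 10% even if one arm loses exactly its two lowest users and the other loses nobody. Larger distortions need four or more one-sided leavers together with a counting rule the plan does not state.

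All of these figures rest on assumed discharge times, assumed day-2 use, and the audit figure read as a 24-hour amount. The endpoint is one secondary outcome of a hypothesis-generating pilot. The 24-hour primary has the same unstated origin, which is resolved in the same way; early discharge touches it only if patients leave before 24 hours.

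### Does the remark that the study procedure comes on top of usual care mean that Group 2 also receives a catheter?

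*Combined protocol and SAP*

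**What the plan says.** There is one document, a combined protocol and SAP. Three places bear on the point.

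- **Introduction.** Usual care is described in these words: "Our standard of care for total shoulder replacement surgeries involves placement of an indwelling interscalene catheter that is attached to an On-Q pump". The same section gives the purpose of the trial, which is to "examine the efficacy of single shot interscalene blocks using Exparel versus the traditional interscalene catheter used at our institution".
- **Design and Methods, arm descriptions.** Usual practice is restated: "At our institution, these patients typically receive an indwelling interscalene catheter and undergo general anesthesia for the surgery". The allocation follows: "group 1 will receive an indwelling interscalene catheter, while group 2 will receive a single shot interscalene nerve block with liposomal bupivacaine". The detailed paragraph for the experimental arm begins "Group 2 will receive a single shot interscalene nerve block using 20 mL of a mixture of 10 mL of Exparel and ten mL of" (the second drug is bupivacaine at 0.5%) and then gives only a sedation limit.
- **Design and Methods, shared care.** After listing the anesthetic and analgesic drugs for all patients, the paragraph ends: "To clarify, the study procedure will be done in addition to standard of care".

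The protocol does not say which care that last sentence means, and it does not define the study procedure.

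**The concern.** The expression for usual care occurs only twice in the document. The first time it is tied to the catheter. The second time the study procedure is said to be added to it, in a sentence offered as a clarification. Substituting the first into the second gives Group 2 a catheter infusion plus a liposomal bupivacaine block. For Group 1 the same substitution is circular, because the assigned intervention is itself the usual care.

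If staff acted on that reading, all 14 planned Group 2 patients would have two sources of local anesthetic. The comparison would become catheter plus liposomal bupivacaine against catheter alone, and the single-shot-against-catheter hypothesis would go untested. A reader on the ethics board might also conclude that Group 2 gives nothing up, although the Introduction ranks continuous catheter infusion as the best method of pain control after this surgery.

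**Working it through.** The check is mainly a comparison of texts, followed by a check on whether any number depends on the sentence.

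**1. What each arm is assigned.**

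| Element | Group 1 | Group 2 |
|---|---|---|
| Indwelling catheter | yes | not listed |
| On-Q pump and rate | yes, 4 mL/hr | not listed |
| Block drug | 15 mL of 0.5% ropivacaine | 20 mL mixture with Exparel |
| Sedation limit for the block | stated | stated, same |

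Nothing in the document assigns a catheter to Group 2. A site following the arm paragraph would have no pump setting to apply there.

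**2. What the rest of the document presupposes.** The title and the purpose statement both set one technique against the other. The Introduction presents the single shot as a way to do without a catheter. The cost argument there makes sense only on that footing. Pump and infusion drug cost \$390 and a vial of Exparel \$285, a saving of 390 − 285 = \$105 if one replaces the other. If both were used, the cost would be 390 + 285 = \$675, and the stated rationale would be reversed.

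**3. What the sentence can mean where it stands.** Its paragraph opens by giving all patients general anesthesia and a common analgesic regimen. It then lists fentanyl, ketamine, acetaminophen, hydromorphone and the PCA. Read as the allocated block added to that background, the sentence is coherent in both arms and the circularity in Group 1 disappears. The Introduction says that usual care *involves* a catheter, which names a component. Design and Methods describes usual practice as a catheter together with general anesthesia. Usual care is therefore wider than the catheter.

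**4. Whether any number depends on it.** Inputs from Statistical Analysis are a mean of 29 mg, SD 12 mg (the ± figure read as an SD), a 50% difference, two-sided alpha 0.05 and power 80%.

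- Difference: 0.50 × 29 = 14.5 mg. Standardized: 14.5 / 12 = 1.21.
- Normal approximation: n = 2(1.96 + 0.84)² / 1.21² ≈ 10.7, so 11 per group and 22 in total.
- Two-sample t-test (noncentral t): 11.79, so 12 per group. The total is 24, as the plan states, with power 80.7%.
- With 14 per group (28 in total), t-test power is 86.8%.

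The plan's figure is reproduced, and rewording the sentence changes none of these inputs.

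**5. What the literal reading would cost if it were followed.** The documents give no expected difference for catheter plus Exparel against catheter. As an illustration only, with SD 12 mg and 14 per group, t-test power is 86.8% for 14.5 mg, 33.7% for half of that (7.25 mg), and equals the 5% alpha for no difference. The loss could be serious, but only if the arm descriptions were disregarded.

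**The case for a change.** The strongest argument for acting is that the sentence calls itself a clarification, and the only content the document ever gives to usual care is the catheter. The shared drug regimen is never labeled that way. No sentence says outright that the catheter is withheld in Group 2; this has to be inferred from the arm descriptions. Replacing usual care and adding to it raise different questions of risk and benefit, and the Risks and Benefits section does not mention forgoing the catheter. The repair is one sentence and costs nothing.

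Part of this stands. The sentence is inconsistent with the Introduction when read literally, and the sponsor should reconcile the two passages. The rest does not carry. A general closing remark does not override specific arm descriptions. The contrast would in any case be altered by the literal reading, not lost. The claim that the ethics board is misled is weak, since the Introduction and Design and Methods state openly that the catheter is usual practice and that Group 2 is allocated a single shot. The consent pages are not in the text available here, so nothing can be inferred about what patients were told. That a repair is cheap does not show that the plan is deficient.

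**Conclusion.** The concern does not call for a change to the plan. It identifies a real but clerical slip: one sentence refers to usual care without saying which part. The comparison is fixed by explicit arm descriptions, and the title, the purpose statement and the cost argument all agree with them. The effect on the primary endpoint, sample size (24, raised to 28) and analysis is nil.

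This rests on two assumptions: that sites follow the arm descriptions, and that the sentence refers to the perioperative care shared by both groups. Nothing in the document points to a different practice. Which description of care holds is for the sponsor to confirm when the wording is tidied.

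### The *Failed block* exclusion is undefined; read as the study block, it removes randomized patients after treatment, and no analysis set overrides it

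*Combined protocol and SAP*

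**What the plan says.** Exclusion Criteria ends with the two words *Failed block*. Nothing says which block, what counts as failure, when it is judged or by whom. Other items do state timing, for example "Pre-existing diabetic neuropathy or Hemoglobin A1c >9".

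Under Randomization, "Subjects will be randomized on the day of the procedure", and "Pre-sealed randomization envelopes will be opened just before performing the block". Allocation therefore precedes the block.

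Statistical Analysis gives the test for the primary endpoint ("24-hour opioid requirements is a continuous variable a nonparametric Wilcoxon rank sum test will" be used) but not the patients to whom it applies. No intention-to-treat, per-protocol or other set is named, and there is no rule for a failed block or a dislodged catheter. The section adds four patients to the calculated 24: "In order to accommodate the missing cases, we are increasing the sample size to 14 patients per group". It does not say whether failed blocks count as missing cases. Under Data Management, "Information in the database will be tracked by the specific randomization code assigned to each patient".

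The Introduction says of the catheter technique that "the catheter is often found to be dislodged from operating room positioning, patient transport or movement". It gives no rate, and nowhere is it said whether dislodgement is a failed block.

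**The concern.** An exclusion that can be applied only after the assigned treatment has been given is not an eligibility rule. It selects patients on an early result of treatment. Block failure plausibly raises opioid use in the next 24 hours, which is the primary endpoint, so the patients removed would tend to be those with high values. If the arms differ in how often blocks fail, or in opioid use after failure, the groups compared are no longer those that randomization formed.

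Because failure is undefined, the decision could also be made with the opioid total in view. With 14 patients per arm, a few such decisions matter.

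**Working it through.** **The plan's own figure.** Inputs from Statistical Analysis: mean 29 mg, SD 12 mg, a 50% difference (0.5 x 29 = 14.5 mg), two-sided alpha 0.05, power 80%. The noncentral-t calculation gives 80.7% power at 12 per arm and 76.9% at 11, so the stated total of 24 reproduces. Four more make 28, or 14 per arm. The sample size is not in error.

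**Timing.** Envelope opened, then block performed, then failure observable. A rule based on the study block must act after randomization. A rule based on a past block could act at screening.

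**Illustration of the shift.** Nothing about failure is given numerically, so these inputs are assumptions: failure rates fc (catheter) and fs (single shot), and excess opioid use e after failure. Working blocks are given means of 29 and 14.5 mg, so the difference after exclusion is 14.5 mg in every case. The shift is the as-randomized difference (catheter minus single shot) minus 14.5, under two models:

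- equal excess in both arms: shift = (fc - fs) x e
- common level of 29 + e after failure in both arms: shift = fc x e - fs x (e + 14.5)

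| fc / fs | e (mg) | Shift, equal excess | Shift, common level | As-randomized difference (mg) |
|---|---|---|---|---|
| 30% / 5% | 24 | 0.25 x 24 = +6.0 | 7.2 - 1.925 = +5.3 | 20.5 / 19.8 |
| 5% / 20% | 24 | -0.15 x 24 = -3.6 | 1.2 - 7.7 = -6.5 | 10.9 / 8.0 |
| 10% / 5% | 12 | 0.05 x 12 = +0.6 | 1.2 - 1.325 = -0.1 | 15.1 / 14.4 |
| 5% / 5% | 24 | 0 | 1.2 - 1.925 = -0.7 | 14.5 / 13.8 |

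Equal failure rates do not guarantee a zero shift. Under the common level with fs = 5% and e = 24, the shift vanishes at fc = 0.05 x 38.5 / 24 = 8.0%. The shifts are in means; the planned test is rank-based, so they indicate direction and scale only.

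**The baseline.** The table treats 29 ± 12 mg as catheters that worked. Statistical Analysis describes it as average use in a clinical audit and does not say that failed or dislodged catheters were left out. If they were included, then at 30% failure and +24 mg the working-block mean would be 29 - 0.30 x 24 = 21.8 mg and the SD sqrt(144 - 0.30 x 0.70 x 24²) = sqrt(23.04) = 4.8 mg. The figures would then change, including the difference left after exclusion and any power derived from these inputs.

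**Numbers lost.** Expected exclusions are 14 x (fc + fs): 1.4 of 28 at 5%/5%, 3.5 at 20%/5% and 4.9 at 30%/5%. The binomial chance that at least one arm falls below 12 is 6%, 57% and 84%. Replacing those patients would restore numbers, not comparability.

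**The case against.** The strongest reply is that *Failed block* stands in an eligibility list in which every other item can be applied before allocation, so a past failed block may be meant. All follow-up is entered and tracked by randomization code, and no sentence says that a randomized patient will be dropped from analysis. This stands to the extent that a reader who infers a settled plan to discard randomized patients goes further than the text. But the past-block reading is not in the text either, and tracking by code does not say who is analysed.

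A second reply is that the larger cases are extreme. An excess of 24 mg is 2 SD and 83% of the audit mean (24/29), the 20% and 30% failure rates have no source in the documents, and blocks are done under ultrasound by a trained expert. That also stands, as does the point about the audit baseline, so the table is an illustration and not an estimate.

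A third reply is that this is a small hypothesis-generating pilot. It nevertheless states a superiority hypothesis, a significance threshold and a powered primary comparison. The four spare patients do not answer the point, because selection after randomization is not a shortage of patients.

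**Conclusion.** The point holds in conditional form and should be fixed before outcomes are seen. An undefined exclusion, taken with the stated timing of randomization and the absence of an analysis set, allows randomized patients to be removed because of how their treatment performed. On the past-block reading there is no such bias; what is missing is the wording and a stated analysis set.

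Size and sign cannot be computed from the documents. In the cases worked, the shift runs from about -6.5 mg (5% catheter, 20% single shot, +24 mg) to +6.0 mg (30%/5%, +24 mg), and is within about 0.7 mg at 5%/5% with +24 mg or 10%/5% with +12 mg. All of this rests on assumed failure rates and excess use, and on reading the audit as working catheters only.

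Two stronger inferences are not supported. A reader might conclude from the remark on dislodgement that exclusion would favour the catheter arm. The documents give no failure rate for either arm and do not equate dislodgement with failure, and the sign reverses if single-shot blocks fail more often. A reader might also take a difference in power with and without failed blocks as the size of the bias. Such contrasts compare different true differences at different sample sizes, so they do not measure it.

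**What to change.** Delete *Failed block* from Exclusion Criteria or, if a past failed block was meant, say so. Add to Statistical Analysis:

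> The primary analysis includes all randomized patients in their assigned arm, regardless of block failure or catheter dislodgement.

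Define block failure before enrolment, with a time and an assessor, and without using the 24-hour opioid total. Report failures and dislodgements by arm. Keep any analysis without failed blocks as a labelled sensitivity analysis.

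This costs a few sentences, one field on the data form and no extra patients. The statistical price is more variable opioid totals. With SD = sqrt(144 + f(1 - f)x²), where x is the excess over that arm's working mean, the single-shot SD at 20% failure is 15.4 mg (x = 24) to 19.5 mg (x = 24 + 14.5 = 38.5). Power is lower when failures are equal in both arms or more common with the single shot. Under the assumptions above, simulated Wilcoxon power with +24 mg is 74-78% as randomized against 82% after exclusion at 5%/5%, and 33-49% against 78% at 5%/20%. Much of the second drop reflects a smaller as-assigned difference (8.0-10.9 mg instead of 14.5), which is what the randomized comparison should then show.
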